4.2.3.3 Description of the trial procedures

4.2.3.2.1 Collection of medical history, demographic and anthropometric data

Medical history includes the previous diseases, concomitant chronic conditions, hereditary issues, social habits (smoking, alcohol or drug abuse), allergological anamnesis, previous surgeries or traumas, occupational history, permanent or periodic drug therapy. Regarding the present condition: date and time of the first signs manifestation, diagnostic and treatment procedures by the screening, their efficacy. A contraception method used by the patient is specified; by signing the Informed Consent Form, the patient agrees to use one of the recommended contraception methods (by the protocol) during the trial and 1 month after the trial completion.

Primary documents must contain data on the sex, age, race, and ethnicity of the patient. A height meter is used to measure the patient's height in centimeters, the weighing scales—body weight in kilograms.

The anthropometric examinations will be conducted in accordance with the Health Risk Monitoring (EHRM) Recommendation for indicators, international collaboration, protocol and manual of operations for chronic disease risk factor surveys, 2002 (17).

Height should be measured in all the patients (the causes which make the height measurement impossible include hair-style peculiarities (e.g., mohawk), patient's refusal to take off a headwear (e.g., turban), patient's incapacity to stand, exceedance of the height meter's scale). The height meter is a vertically positioned panel with a centimeter division with a sliding horizontal ruler. A standard error must not exceed 2 mm. The patient will be asked to take off his/her shoes, thick clothes, hairpins, or other hair accessories. The patient must touch a vertical panel with his/her hindhead, back, buttocks, calves, and heels (the toes are stuck together). Upper boundary of the external ear canal must be at the same level with lower boundary of the orbital cavity (the jugal bone). The patient will be asked to look forward. If the patient's height exceeds that of the Investigator, the latter should use a platform. A height meter's ruler is put on the patient's head, the scale's divisions are counted. The height must be recorded while the patient is still standing under the ruler. An error must not exceed 0.5 cm.

The patient's weight must be measured in the morning in the fasting condition, after urination and defecation, in the underwear (with further subtraction of an average underwear weight). The weighing scales must be horizontally positioned on a solid ground. An error must not exceed 0.2 kg. The patient should stand in the center of the weighing scales on both legs. If the weight measurement is impossible, the Investigator should not record any values based on the patient's claims.

Protocol No. TE_004_ANG_LOZ

4.2.3.2.2 Physical examination and vital signs evaluation

Physical examination will be conducted according to the general rules of the propedeutics of internal diseases: general visual examination, inspection of the mucous membranes, including pharyngoscopy, lymph nodes palpation, evaluation of bones and muscles, palpation, percussion and auscultation of the main organ systems (cardiovascular, respiratory, gastrointestinal, urinary systems) will be conducted sequentially.

Vital signs (HR, BR, BP, body temperature) will be evaluated before the physical examination at rest (after 15 minutes of rest, not earlier than 1 hour after smoking or 2 hours after meal). Heart rate (HR) will be measured during the heart auscultation in parallel with a pulse rate determination on the radial artery (or carotid artery in case the radial artery pulse is weak) for 1 minute in a sitting position; in case of a pulse deficiency, both parameters should be recorded: HR and pulse rate. Breathing rate (BR) will be measured for 1 minute at rest, in a sitting position, observing breathing movements of the thorax and abdominal wall without drawing the patient's attention.

Blood pressure (BP) will be measured on the brachial artery, in a sitting position, by Korotkoff method, using a certified sphygmomanometer or tonometer with a cuff adjusted for the patient's shoulder in length and width according to the recommendations for measurement (RMOAG/VNOK, 2010). The cuff's size should correspond to the arm's size: a cuff rubber part to be inflated should cover not less than 80% of the arm circumference; a cuff 12−13 cm in length and 30−35 cm in width (medium size) should be used for the adults; although, the bigger and smaller cuffs might be required for bigger and smaller arms, respectively. Before the measurement start, a mercury column or a tonometer needle must be in a zero position. To measure BP on every arm not less than 2 measurements with a 1-minute interval are required; in case of BP difference ≥5 mm Hg, an additional measurement should be made; the lowest result based on the 3 measurement should be recorded as a final one.

Measurement procedure:

- Pump up the air into the cuff fast to the pressure level 20 mm Hg exceeding a common systolic BP (by the pulse disappearance).
- An error must not exceed 2 mm Hg.
- Reduce the pressure in the cuff at a rate of 2 mm Hg per second.
- A pressure level when the 1st tone appears corresponds to a systolic BP (phase 1 of Korotkoff sounds).
- A pressure level when the tones disappear corresponds to a diastolic BP (phase 5 of Korotkoff sounds); in children, adolescents, and young people after physical exertion, in pregnant women, as well as in some disorders in adults when phase 5 cannot be determined, a healthcare practitioner should try to determine phase 4 by significant tones weakening.

- If the tones are very weak, the patient should raise his/her hand and make several compressions by hand, after which the measurement should be repeated without a strong compression on the artery by a phonendoscope membrane.
- BP should be measured on both hands at initial examination only; further measurements must be performed at the hand with higher values.

Body temperature must be measured by the same thermometer type (mercuric or electronic) and method (axillary temperature) throughout the trial.

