 - Severe (IV acc. to Canadian Cardiovascular Society) or unstable angina; a.
 - Decompensated chronic heart failure (NYHA stage IV); b.
 - Myocardial infarction for the last 6 months; c.
 - Uncontrolled arterial hypertension (BP more than 180/115 mm Hg). d.

- 24. Pregnant and/or breastfeeding women.
- 25. Participation in other clinical trials at the screening visit or for 30 days before the screening visit.
- 26. Surgical intervention for 30 days before the screening visit or planned surgical treatment during the trial (before a follow-up visit is completed), including diagnostic procedures or hospital stay.
- 27. Known or suspected narcotic/alcohol abuse.
- 28. A suspected low compliance or incapability of the patient to perform the procedures and comply with restrictions according to the trial protocol (e.g., due to mental disorders).
- 29. Any cardiovascular, renal, hepatic, gastrointestinal, endocrine, or nervous disorders, or any other conditions/diseases which, in the Investigator's opinion, might inflict harm to the patient's health.

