9.1.4 Safety parameters analysis

A descriptive part of the safety analysis will include an evaluation of incidences and two-sided CI 95% for the following parameters in every trial group:

- AEs: the incidence in total and for separate categories (according to MedDRA), for the trial and by groups;
- SAEs: the incidence in total and for separate categories (according to MedDRA), for the trial and by groups;
- Incidence of clinically significant changes of the physical examination results by visits and groups;
- Incidence of clinically significant changes of the laboratory results by visits and groups;
- Incidence of clinically significant changes of the vital signs (body temperature, BP, pulse rate, HR) by visits and groups;
- Incidence of clinically significant changes of the ECG parameters by visits and groups;
- Global tolerance evaluation during the trial by the Investigator and patient.

The Fisher's exact test will be used to compare incidences between the groups, and chi-square will be used to compare the global therapy tolerability by the Investigator and patient. The McNemar's test will be used to evaluate for the dynamic changes during the trial (before—after) for all the repeatedly evaluated incidences in every group.

In addition to the incidence, all the quantitative safety parameters will be presented in a table form (laboratory results, vital signs, ECG) by visits and groups. The difference will be evaluated using 2-way-ANOVA (group and visit numbers will serve as the relevant factors). The post-hoc criteria will be used in case of significant difference.

Safety analysis will be performed on the safety population.

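### Recording the lowest of three blood-pressure readings when the first two disagree biases recorded levels downward in patients with variable readings and makes changes from baseline noisier

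*Protocol*

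**What the plan says.** Protocol section 4.2.3.2.2 sets one method for all visits. It begins: "To measure BP on every arm not less than 2 measurements with a 1-minute interval are required". If the readings differ by 5 mm Hg or more, "an additional measurement should be made; the lowest result based on the 3 measurement should be recorded as a final one". It does not say what is recorded when the two readings differ by less than 5 mm Hg. Both arms are measured at the initial examination only; afterwards the arm with the higher values is used.

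The recorded value is used in three ways:

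- **Screening.** Protocol section 5.2, criterion 23d: "Uncontrolled arterial hypertension (BP more than 180/115 mm Hg".
- **Levels by visit.** SAP section 4.1.1 and the Table 7 template describe blood pressure at Visits 1, 2 and 3.
- **Safety comparisons.** Protocol section 9.1.4 plans "Incidence of clinically significant changes of the vital signs (body temperature, BP, pulse rate, HR) by visits and groups", with no numeric cut-off, and a two-way ANOVA with group and visit as factors. SAP section 4.1.5 adds between-group comparisons of changes and paired within-group tests.

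The same paragraph describes the adult cuff: "a cuff 12−13 cm in length and 30−35 cm in width (medium size) should be used for the adults". It also says that the inflatable part "should cover not less than 80% of the arm circumference".

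**The concern.** The minimum of several readings is a biased and noisier estimate of a patient's pressure than their mean. Here the minimum is taken only when the first two readings disagree, so the size of the bias depends on how variable the patient is. Two patients with the same true pressure can receive systematically different recorded values, and the more variable one is recorded lower.

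Against an absolute limit nothing offsets this: a patient whose true pressure is above 180/115 is more likely to be recorded at or below it. In comparisons of change, the extra measurement error makes real differences harder to see, in a trial whose stated objective includes non-inferior safety.

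**Working it through.** The plan gives no figure for blood-pressure error, so there is none to reproduce. The rule was simulated with 1,000,000 or more patients per setting.

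**Inputs from the documents:** at least two readings; third reading at a difference of 5 mm Hg or more; lowest of three then recorded; screening limit 180 mm Hg systolic.

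**Assumptions:** readings are independent and normal around the patient's true pressure, without trend; the SD of a single reading, σ, is 3 to 8 mm Hg; the mean of two is recorded when they differ by less than 5. The comparator is the mean of all readings taken.

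**Step 1. How often the rule acts.** The difference of two readings has SD σ√2, so P(trigger) = 2[1 − Φ(5/(σ√2))]. At σ = 5, 5/7.07 = 0.707 and P = 2(1 − 0.760) = 0.48.

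**Step 2. Bias and error of the recorded level.** Overall bias = P(trigger) × bias when triggered, because the bias is zero otherwise. At σ = 5: 0.480 × (−5.46) = −2.62 mm Hg.

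| σ | Triggered | Bias when triggered | Overall bias | Error SD, plan | Error SD, averaging |
|---|---|---|---|---|---|
| 3 | 24% | −3.9 | −0.9 | 2.70 | 2.04 |
| 5 | 48% | −5.5 | −2.6 | 4.50 | 3.24 |
| 6 | 56% | −6.3 | −3.5 | 5.31 | 3.83 |
| 8 | 66% | −7.9 | −5.2 | 6.90 | 5.00 |

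Averaging has zero bias throughout. If the lower of two were recorded below the 5 mm Hg trigger, the overall bias would be −1.8, −3.2 and −5.6 at σ = 3, 5 and 8.

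**Step 3. Screening.** For a true systolic pressure of 185, the recorded value exceeds 180 in 61% of cases under the plan and 91% with averaging at σ = 6 (81% and 97% at σ = 4). For a true 184 at σ = 5, the patient passes in 38% of cases under the plan and 11% with averaging. These figures use one arm. If the higher of two arms is tested, with equal true pressure and independent readings in each, the pass rates become 0.38² = 14% and 0.11² = 1%.

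**Step 4. Change from baseline.** With equal σ at both visits the bias subtracts out: a true rise of 20 is recorded on average as 20.0 under both rules. The error SD of a change at σ = 5 is √2 × 4.50 = 6.4 under the plan and √2 × 3.24 = 4.6 with averaging, a ratio of error variances of (4.50/3.24)² = 1.93.

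The plan gives no cut-off for a rise, so 20 mm Hg or more is used as an illustration at σ = 5. A true rise of 10 is counted in 5.8% under the plan and 1.5% with averaging. A true rise of 25 is counted in 78% and 86%. Counts move in both directions.

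**Step 5. Cuff.** Coverage of 80% with a 12 to 13 cm length is possible only for arms up to 12/0.8 = 15 cm to 13/0.8 = 16.25 cm in circumference. The 30 to 35 cm dimension fits the coverage rule, so the two words appear to be exchanged.

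**The case against.** A reader might infer that rises in blood pressure are under-counted in the safety analysis. The documents do not support this. Protocol section 9.1.4 and SAP section 4.1.5 work mainly on changes, the same rule applies at every visit, and step 4 shows that mean change is unbiased when variability is equal. An under-count would need a fixed post-baseline cut-off, which the plan does not set, or variability that increases after baseline.

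A reader might also infer a bias between arms. If σ rose from 5 to 8 in one arm, a spurious fall of about 2.6 mm Hg would appear there (−5.21 against −2.62). Nothing in the documents suggests that either spray makes pressure more variable, and both arms follow the same rule.

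The screening effect can also be overstated. Criterion 23 leaves room for the investigator's opinion, the investigator sees every reading, and both arms are measured at the first examination. The documents do not say which arm's value is tested. They also give no indication of how many patients aged 18 to 45 with an uncomplicated sore throat would be near 180/115. These points shrink the harm but leave a gap between the two rules (14% against 1% in the two-arm case).

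Finally, independence without trend is an assumption. If pressure falls as the patient settles, the lowest reading need not understate resting pressure. The section cites an external recommendation for measurement, and whether it prescribes this rule cannot be judged from the documents.

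**Conclusion.** The point holds in a limited form and is minor. Under independent readings without trend, the rule lowers the recorded level in patients with variable readings and leaves it unbiased in the others. Only the size depends on the assumed SD; the direction does not. The consequences are under-detection of high absolute values at screening and in by-visit tables, and noisier changes from baseline. The variance ratio in step 4 concerns measurement error only; true differences between patients add to both sides, so the loss of precision in the group comparisons is smaller than that ratio.

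Blood pressure is neither a primary nor a secondary efficacy endpoint, and SAP section 4 confines the non-inferiority conclusion to the primary parameter, so the trial's main conclusion does not depend on this rule. The cuff wording is an editorial slip and carries no weight in this assessment.

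**What to change.** In Protocol section 4.2.3.2.2, replace the lowest-of-three instruction. The recorded value should be the mean of all readings taken on the arm used: two readings, or three when the first two differ by 5 mm Hg or more. The same rule should apply at Visits 1, 2 and 3. The section should also name which arm's value counts at Visit 1, where both are measured. Use the recorded mean for criterion 23d (22d in the synopsis) and for the vital-sign analyses in Protocol section 9.1.4 and SAP sections 4.1.1 and 4.1.5. Reconcile the cuff length and width with the 80% coverage rule as an editorial correction.

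The cost is small. The readings are already taken, so no measurement is added. Recorded pressures will be slightly higher, and a few borderline patients may fail screening.

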4.2.3.2.3 Fill-in of TSS questionnaire

TSS, a questionnaire (point scale) for healthcare professionals, is used in clinical practice as well as in clinical trials to evaluate dynamic changes of symptoms severity of the infection and inflammatory process in the throat (Bereznoy VV, Riley DS, Wassmer G, Heger M. Efficacy of extract of Pelargonium sidoides in children with acute non-group A beta-hemolytic streptococcus tonsillopharyngitis: a randomized, double-blind, placebo-controlled trial). One of such clinical trials with TSS questionnaire was conducted in 2005 in Germany, ©CRO Applertee AG. A version of TSS ©CRO Applertee AG was adapted for this protocol.

TSS (Tonsillopharyngitis Severity Score) is a questionnaire for evaluation of the following symptoms severity: pharyngalgia, difficulty in swallowing, salivation, hyperemia of pharyngeal mucosa, and body temperature increase according to a 4-point scale:

- 0 = no symptom;
- 1 = insignificant symptom;
- 2 = moderate symptom;
- 3 = significant symptom.

The axillary body temperature increase is rated as follows:

- 0 points: <37.5 °C;
- 1 point: 37.5 to <38.5 °C;
- 2 points: 38.5 to <39.5 °C;
- 3 points: >39.5 °C.

TSS is filled in by the Investigator based on the patient complaints and physical examination data. The Investigator summarizes the points obtained for every symptom to obtain a total sum of TSS points. A total sum of TSS points will be used at screening to evaluate for a subject's eligibility and baseline evaluation; on Visit 2 (Day 4), to measure efficacy of the trial therapy in both groups; to evaluate the disease outcomes at Visit 2 (Day 4) and/or Visit 3 (Day 5), where applicable.

4.2.3.2.4 Evaluation of the throat pain intensity according to VAS

The patient will fill in the VAS to evaluate for the throat pain intensity at every visit to the trial site (Visit 1, Visit 2, and Visit 3 (where applicable)). Calibrated scales 100 mm in length with the relevant measuring instruments will be provided for the clinical trial.

The patients should evaluate their pain severity according to VAS at every visit (if possible, before administration of the painkillers (if those are required) or the study drug/comparator drug). The scale is provided in Appendix 5 to this protocol.

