Lidocaine absorption varies depending on the site and the method of administration. It is rapidly absorbed from the gastrointestinal tract, mucous membranes and through broken skin; however, before entering the systemic circulation it is mostly decomposed. The absorption from mucous membranes after topical application depends on the circulation and the total dose. After 30 minutes, less than 17% of the dose is present in the stomach and the intestines in the unchanged form, while less than 1.5% is present in other tissues.

The anesthetic action of lidocaine after topical administration emerges after two to five minutes and lasts for 30 to 45 minutes. The anesthetic effect is limited to the surface and does not extend to the submucosal structures.

Distribution

Lidocaine is well distributed into tissues (kidney, lung, liver, heart, adipose tissue).

Lidocaine crosses the blood-brain barrier and placenta and is excreted in human milk.

Metabolism and elimination

It is metabolized during the first pass through the liver. Lidocaine undergoes dealkylation in the liver. The first two metabolites are pharmacologically active. These two active metabolites exert toxic effects on the central nervous system in some patients.

Lidocaine is eliminated in the form of metabolites through the kidneys. Approximately 10% is eliminated unchanged. The biological half-life of lidocaine is 1.5 to 2 hours in adults. The biological elimination half-life of lidocaine metabolites is

two to ten hours. The biological half-life is increased in congestive heart failure, liver diseases, and myocardial infarction.

Pharmacological properties

Angal S, topical spray, contains two active substances. The first is chlorhexidine, a bisbiguanide antiseptic, with an antimicrobial effect on gram-positive and gram-negative bacteria, especially in the vegetative form (it is not effective against spores at normal temperature). It exerts an antimycotic effect on dermatophytes and fungi. It quickly inactivates the infectiousness of certain lipophilic viruses (influenza virus, herpes virus, HIV). The susceptibility of individual bacterial strains varies. The drug exerts bacteriostatic effects in low levels and bactericidal effects in high levels.

The second active substance of Angal S, topical spray, is lidocaine, an amide local anesthetic. It exerts local anesthetic effect.

Therapeutic indications

Angal S spray has double action (antimicrobial and analgesic), therefore, it is used for:

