2.1.2 Reference drug

ANTI-ANGIN® FORMULA, metered topical spray, 0.12 mg + 0.24 mg

ATC code: R02AA20 **Pharmacological groups**

- Local anesthetics in combinations
- Antiseptics and disinfectants in combinations

Composition and presentation

Lozenges	1 dose
tetracaine hydrochloride	0.12 mg
chlorhexidine digluconate	0.24 mg
Excipients: glycerol 85%—60.00 mg, ethanol 96%—80.00 mg, aspartame 0.20 mg propylparahydroxybenzoate—0.20, anhydrous citric acid—up to 200 mg.	,

Pharmaceutical form

Metered topical spray. 25 ml of the drug (100 doses) are placed in a plastic bottle with a dosing valve in a carton pack with Prescribing Information.

Description of dosage form

Spray: a plastic vial with a dosing valve. Vial content: colorless mint-flavored liquid.

Pharmacological properties

Pharmacological effects: antiseptic and local anesthetic. Pharmacodynamics

Chlorhexidine exerts the bactericidal and bacteriostatic effects.

It has a wide spectrum of antibacterial activity against gram-positive and gram-negative bacteria as well as *Candida albicans*. Chlorhexidine is especially effective against *Streptococcus mutans*, *Streptococcus salivarius*, *Escherichia coli*, and anaerobic bacteria. It is less effective against *Streptococcus spp.*, *Proteus spp.*, *Pseudomonas spp.*, *Klebsiella spp.*, *Veillonella spp.*

Tetracaine acts as a local anesthetic. An anesthetic effect develops 1–2 minutes after the drug use.

Indications

Prevention, causal and symptomatic treatment of inflammatory infections of oral cavity and throat caused by chlorhexidine-sensitive bacteria (pharyngitis, tonsillitis, peritonsillar abscess at early stages, parodontosis, stomatitis, gingivitis, post-tonsillectomy or dental extraction conditions, etc.). Complex therapy of peritonsillar abscess (should be used at first symptoms, i.e., pharyngalgia and irritation).

Contraindications

Hypersensitivity to the components of the drug, mucosal lesions or inflammation, hypervascularization, phenylketonuria, pediatric use (under 10 years old).

Special precautions for use:

Pregnancy and lactation, diabetes mellitus, glucose-6-phosphate dehydrogenase deficiency, hemochromatosis, sideroblastosis anemia, thalassanemia, hyperoxaluria, oxalosis, and urolithiasis.

Posology and method of administration

Topically. While breath is held, the drug should be sprayed on oral and pharyngeal mucous membranes.

Adults: 1–2 sprays at a time, up to 6 times a day.

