4.2.4.3 Trial completion visit for Group B patients (Visit 3, Day 5)

This visit is for Group B patients only (ANTI-ANGIN® FORMULA) who did not achieve the recovery criteria (total TSS score ≤ 2) at Visit 2 (Day 4).

Visit 3 is conducted on Day 5; the patient must visit the trial site in the fasted state and bring the filled-in diary and unused drug.

Visit 3 procedures:

- Collection of complaints, actualization of anamnesis;
- Records on the concomitant therapy;
- Physical examination (including oropharynx);
- Measurement of the main vital signs;
- Evaluation of adverse events (including based on results of the throat and pharynx examination);
- Evaluation of exclusion criteria;
- Return of the unused study drug;
- Return of the patient's diary;
- Compliance evaluation (diary completion, administration of the study drugs);
- Hematology:
- Biochemistry;
- 12-lead ECG;
- Global evaluation of treatment tolerability during the trial by the physician and the patient.

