6.3 Methods to monitor the subjects' compliance with trial procedures

At every visit after Visit 1, the subjects' compliance will be checked by counting the unused drug and analysis of the patient's diaries.

The protocol envisages the dose of Angal S, the study drug, as 3 to 5 consecutive presses on the actuator button, 6 to 10 times per day, and ANTI-ANGIN® FORMULA, the comparator drug, 1–2 sprays up to 6 times per day with not less than a 2-hour intervals between the doses. Both drugs should be taken when needed (a sore throat).

In view of the nature of drug intake (when needed), the lower margin of compliance will not be evaluated; the number of used doses is compared to maximum amounts stated in the protocol for the study drug (up to 5 sprays at once, not more than 10 times per day for Angal) or Prescribing Information for the comparator drug (up to 2 sprays at once, not more than 6 times per day for ANTI-ANGIN® FORMULA).

List of efficacy parameters

7 Efficacy evaluation

Primary outcome measure

7.1

The primary outcome measure was the percentage of patients without sore throat after 3 days of therapy, as evaluated by the Investigator according to the Tonsillopharyngitis Severity Score (TSS), in both Angal S and ANTI-ANGIN® FORMULA arms.

Secondary outcome measures

The secondary outcome measures in both therapy groups were:

- Frequency of ≥50% total score reduction according to the TSS questionnaire completed by the Investigator as compared to the baseline in both Angal S and ANTI-ANGIN® FORMULA groups at Visit 2 (Day 4).
- Total score reduction according to the TSS questionnaire, as well as a reduction in the symptoms (sore throat, difficulty in swallowing, salivation, erythema, and fever) after a 3-day therapy, at Visit 2 (Day 4), as compared to the baseline total score.
- A period of time required for disease symptoms relief, determined according to the patient's diary (subjective patient's evaluation), but no more than 5 days during the trial—for patients who have achieved the corresponding outcome.
- A proportion (%) of patients who fully recovered by Day 4 in Group A and by Day 5 in Group B (the outcome of a disease according to the objective evaluation by the Investigator, the total score according to the TSS questionnaire ≤2).
- A change in the sore throat intensity by 100 mm VAS (visual analogue scale filled in by the patient) at the beginning, after 3 days of therapy, and at the end of treatment in both groups.

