7.2 Methods and timing for evaluation, recording, and analysis of efficacy parameters

The methods for efficacy criteria evaluation are described in Section 4.2.3.2. The first endpoint is evaluated in the morning at Visit 2 (Day 4, after 3 days of the trial therapy) before the study drugs intake. Other efficacy endpoints are evaluated in terms stated in Section 7.1.

8 Safety evaluation

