16.2 Appendix 2. TSS (Tonsillopharyngitis Severity Score) questionnaire

TE_003_ANG_LS	P	TONSILLOPHARYNGITIS SEVERITY SCORE (TSS)			PATIENT No.	PATIENT No.	
Visit*	Evaluation point	Discomfort severity*	SORE THROAT	DIFFICULTY IN SWALLOWING	SALIVATION	PHARYNGEAL MUCOSA HYPEREMIA	BODY TEMPERATURE INCREASE**
VISIT 1	BASELINE	no symptom					
		insignificant symptom					
		moderate symptom					
		significant symptom					
VISIT 2	AFTER 3 DAYS OF	no symptom					
	THERAPY	insignificant symptom					
	evaluation before the first intake	moderate symptom					
	of the study drug on Day 4	significant symptom					
VISIT 2/3	DISEASE OUTCOME*	no symptom					
		insignificant symptom					
		moderate symptom					
		significant symptom					
* To be filled-in by the Investig	ator at a Visit. The disease outcome: applicable	e, if TSS > 2 after 3 days of therapy.					
Answers rate in points 0 = no symptom; 1 = insignificant symptom; 2 = moderate symptom; 3 = significant symptom.				** The axillary body temperat 0 = <37.5 °C 1 = 37.5 to <38.5 °C 2 = 38.5 to <39.5 °C 3 = ≥ 39.5 °C	ture increase is rated as follows:		
Investigator (Full name/Signa	ature)				Date		

Version 1.0 of September 29, 2016 in Russian, compiled based on the final version of November 21, 2005 in German. © Appletree AG

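### Secondary endpoints: VAS need precede the spray only where possible, and Group B's Visit 3 recovery TSS has no pre-spray rule, so a numbed throat can be scored

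*Protocol*

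**What the plan says.** **VAS.** Protocol 4.2.3.2.4 and SAP 2.2 use the same wording: the patient scores pain at each visit, "if possible, before administration of the painkillers (if those are required) or the study drug/comparator drug".

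**TSS and the other endpoints.** Protocol 7.2 fixes the primary score in the morning of Visit 2, before study drug. For the rest it says "Other efficacy endpoints are evaluated in terms stated in Section 7.1". Section 7.1 names days and visits but gives no timing relative to a dose.

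**TSS form (Appendix 2).** The Day 4 row carries the instruction "evaluation before the first intake". The disease-outcome row, which applies "if TSS > 2 after 3 days of therapy", carries no such instruction. The form has a date field but no time field.

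**Visit 3 (4.2.4.3).** Only Group B patients with total TSS above 2 on Day 4 attend. They come fasted and "bring the filled-in diary and unused drug". Nothing bars a spray earlier that morning. Table 1 schedules both VAS and TSS at this visit.

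**Dosing (6.3).** "Both drugs should be taken when needed (a sore throat").

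**Anesthetic action.** For tetracaine (Group B), 2.1.2 says: "An anesthetic effect develops 1–2 minutes after the drug use". Its duration is not stated. For lidocaine (Group A), 2.1.1 says: "The anesthetic action of lidocaine after topical administration emerges after two to five minutes and lasts for 30 to 45 minutes".

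**Role of these endpoints.** SAP section 4 rests the non-inferiority conclusion on the primary parameter alone and treats the secondary variables as exploratory.

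**The concern.** Both products numb the throat within minutes. The plan guards the primary score against this by requiring it before the dose. The same sore-throat item enters the recovery score (total TSS of 2 or less), and the VAS measures the same symptom, yet neither has equal protection.

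The gap is clearest at Visit 3. The patients seen there still have symptoms, are told to spray when the throat hurts, and carry the spray with them. A site following the protocol to the letter could score such a patient a few minutes after a dose.

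Two secondary results are at stake:

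- **VAS change.** Visit 1 lists the VAS before the drug is dispensed, so the baseline is clean. A later score taken after a spray would overstate improvement. At Visit 2 this could happen in either arm, so the net direction is not known.
- **Recovery proportion.** Only Group B has a Visit 3, so a numbed score there can add recoveries only to the comparator arm.

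**Working it through.** The plan gives no figure for this point, so there is nothing to reproduce. The steps below ask whether numbing can change the recovery classification, and roughly how often.

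**1. Can the threshold be crossed?** Recovery is total TSS of 2 or less. Take sore throat 1, swallowing 1, salivation 0, hyperemia 1 and temperature 0: the total is 3, not recovered. If the spray takes pain and swallowing to 0, the total is 1, recovered. So it can.

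**2. How many score patterns could cross?** With the temperature item at 0, four items scored 0 to 3 give 4^4 = 256 patterns. Of these, 1 + 4 + 10 = 15 have a total of 2 or less, leaving 241 above 2.

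- Pain and swallowing both go to 0: the pattern crosses if salivation + hyperemia is at most 2. That is 6 × 16 = 96 patterns, less the 15 already at 2 or below = 81. 81/241 = 33.6%.
- Each drops one point (floor 0): 16 of the 20 patterns at total 3 cross, and 10 of the 31 at total 4. 26/241 = 10.8%.

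**3. What share of the day might the throat be numb?** Inputs: at most 6 comparator doses a day (6.1), 30 to 45 minutes each (lidocaine's figure, borrowed because tetracaine's is not given), and a 16-hour, 960-minute waking day (assumption).

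- 6 × 30 / 960 = 18.75%
- 6 × 45 / 960 = 28.1%

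**4. Share of Group B's non-recovered patients misclassified (f)** = numb share × crossing share.

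- Low: 0.1875 × 0.108 = 2.0%
- High: 0.281 × 0.336 = 9.5% (9.45% before rounding)

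**5. Shift in the recovery difference (A minus B)** = −(1 − p) × f, where p is the recovery proportion without numbing. The documents give no p, so a range is shown.

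| p (assumed) | f = 2.02% | f = 9.45% |
|---|---|---|
| 60% | −0.8 points | −3.8 points |
| 70% | −0.6 points | −2.8 points |
| 80% | −0.4 points | −1.9 points |

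At p = 70% with 140 per arm, 42 Group B patients are not recovered. The misclassified number is 42 × 0.0202 = 0.8 to 42 × 0.0945 = 4.0 patients.

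**6. Limits of this range.** It is an indication, not a bound. The 241 patterns are unweighted and include totals up to 12. Visit 3 patients may sit nearer the cutoff, which would raise the crossing share. Six doses a day is the maximum, and few sprays will precede a morning visit, which would lower the numb share.

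**7. Can late scores be found afterwards?** The diary records the time of each spray on Days 4 and 5 (Appendix 3), and the VAS form has a time field (Appendix 4), so VAS timing can be checked. The TSS form has only a date. The same-visit VAS time is a proxy at best.

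**The case against.** **Much is already covered.** The Day 4 TSS must precede the first spray, and the Visit 2 VAS is taken at the same visit, so it will usually be pre-spray too. That stands, but it makes a clean Visit 2 VAS likely, not required, and it does nothing for Visit 3.

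**The recovery comparison has a larger imbalance in the same direction.** Group A is read on Day 4 and Group B on Day 5, so genuine recovery over that extra treated day also favours the comparator. This stands. A reader might infer that numbing substantially raises the chance of a significant Fisher test favouring the comparator. With 140 per arm and equal true rates of 70%, that chance does go from 1.8% to 3.5% at f = 5% and 6.2% at f = 10%. But equal rates would hold only if nobody in Group B recovered between Day 4 and Day 5. If 20% of the non-recovered truly did (assumption), the chance is already 16.8% with no numbing. These figures therefore do not measure the effect of the timing gap.

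**Stronger readings the documents do not support.**

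- *A 20% misclassification rate.* It would need nearly all Visit 3 patients just above the cutoff and scored at the maximum numb share. Neither is shown.
- *VAS numbness recorded as recovery.* VAS does not define recovery; only TSS does.
- *Group A equally exposed on TSS.* Its outcome score falls at the same visit as its pre-spray score, and the drug is handed back there.
- *Damage to the primary endpoint.* It has its own pre-dose rule, so nothing here calls for a new primary sensitivity analysis.

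**The painkiller wording.** The VAS text allows for painkillers, which 6.2.2 prohibits. Exclusion criterion 11 and SAP 3.2 already deal with patients who take them, so this is an editorial mismatch only.

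**Conclusion.** The gap in the text is real, and a compliant site could score a numbed throat. The confidence is in the wording, not in the size of the effect.

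The effect is confined to secondary endpoints. For VAS it is overstated improvement, net direction unknown. For recovery it favours the comparator, so it works against the study drug. A rough figure is 0.6 to 2.8 points at an assumed 70% recovery rate. It rests on a borrowed lidocaine duration, a 16-hour day, maximum dosing and unweighted score patterns; the true size is unknown. It adds to the separate Day 4 versus Day 5 imbalance, which better timing would not remove. The non-inferiority conclusion does not change. Severity is minor: a cheap improvement rather than a flaw in the main analysis.

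**What to change.** - In protocol 4.2.3.2.4, 7.2 and Appendices 2 and 4, and in SAP 2.2, delete *if possible* and require every Visit 2 and Visit 3 VAS and TSS score, including the disease-outcome row, before that day's first spray.
- Add a clock-time field to the TSS form.
- If a patient has already sprayed, keep the score and flag it using the diary spray time.
- As an editorial change, align the painkiller wording in 4.2.3.2.4 and SAP 2.2 with 6.2.2.

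The cost is wording, a site instruction and one form field. The Visit 3 patient waits until the visit for the morning spray, as the primary-endpoint rule already requires at Visit 2. No patients, visits or changes to the main analysis are added.
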